9.1.11 Contraception and Pregnancy Avoidance Procedure

From signing of the ICF throughout the duration of the study and for 30 days after last dose of study drug, nonsterilized** male subjects who are sexually active with women of childbearing potential* must use double-barrier contraception (eg, condom with spermicidal cream or jelly). In addition, they must be advised not to donate sperm during this period.

From the signing of the informed consent, throughout the duration of the study, and for 30 days after last dose of study medication, women of childbearing potential* who are sexually active with nonsterilized men** must use adequate contraception. In addition they must be advised not to donate ova during this period.

*Women NOT of childbearing potential are defined as those who have been surgically sterilized (hysterectomy, bilateral oophorectomy, or tubal ligation) or who are postmenopausal (eg, defined as at least 1 year since last regular menses with an FSH>40 IU/L or at least 5 years since last regular menses, confirmed before any study medication is implemented).

**Sterilized men should be at least 1 year postvasectomy and have confirmed that they have obtained documentation of the absence of sperm in the ejaculate.

An acceptable method of contraception is defined as one that has no higher than a 1% failure rate. In this study, where medications and devices containing hormones are included, the only acceptable methods of contraception are:

Barrier methods (each time the subject has intercourse) where applicable*:

- Cap (plus spermicidal cream or jelly) PLUS male condom and spermicide.
- Diaphragm (plus spermicidal cream or jelly) PLUS male condom and spermicide.

Intrauterine devices (IUDs):

- Copper T PLUS condom or spermicide.
- Progesterone T PLUS condom or spermicide.

Hormonal contraceptives:

- Implants.
- Hormone shot/injection.
- Combined pill.
- Minipill.
- Patch.
- Vaginal ring PLUS male condom and spermicide.

*Barrier methods is only applicable in countries where spermicide is commercially available.

Subjects will be provided with information on acceptable methods of contraception as part of the subject informed consent process and will be asked to sign a consent form stating that they understand the requirements for avoidance of pregnancy, donation of ova, and sperm donation during the course of the study.

During the course of the study, regular hCG pregnancy tests will be performed only for women of childbearing potential and subjects will receive continued guidance with respect to the avoidance of pregnancy and sperm donation as part of the study procedures ([Appendix A](#)). In addition to a negative serum and urine hCG pregnancy test at Screening, subjects also must have a negative serum and urine hCG pregnancy test at Day -1.

9.1.12 Pregnancy

If any subject is found to be pregnant during the study she should be withdrawn and any sponsor-supplied drug (dexlansoprazole 30, 60 mg, lansoprazole 30 mg, and matching placebo) should be discontinued immediately. In addition, any pregnancies in the partner of a male subject during the study or for 30 days after the last dose should be recorded following authorization from the subject's partner.

If the pregnancy occurs during administration of active study medication, eg, after Visit 2 or within 30 days of the last dose of active study medication, the pregnancy should be reported immediately, using a pregnancy notification form, to the contact listed in Section 1.0.

Should the pregnancy occur during or after administration of blinded drug, the investigator must inform the subject of their right to receive treatment. If the subject chooses to receive unblinded treatment information, the individual blind should be broken by the investigator. Subjects randomized to placebo need not be followed.

If the woman subject and/or woman partner of a man who is a subject agrees to the primary care physician being informed, the investigator should notify the primary care physician that the subject/woman partner of the subject was participating in a clinical study at the time she became pregnant and provide details of treatment the subject received (blinded or unblinded, as applicable).

All reported pregnancies will be followed up to final outcome using the pregnancy form. The outcome, including any premature termination, must be reported to the sponsor. An evaluation after the birth of the child will also be conducted.

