At the Week 8 Visit, all subjects will undergo a physical examination including vital signs, laboratory evaluations, fasting serum gastrin, serum and urine pregnancy test (all women of childbearing potential), ECG and an endoscopy. In addition, study drug will be collected, a review of concomitant medication use will be performed, and an assessment of AEs will be conducted. If the subject's EE has healed completely as determined by endoscopy, the subject will have completed the Healing Period of the study, and will continue in the Maintenance Period. If the subject's EE has not completely healed after 8 weeks of treatment, all Final Visit procedures will be performed and the subject will not be eligible to continue into the Maintenance Period.

For subjects who prematurely discontinue during the Healing Period, efforts should be made to perform all procedures scheduled for the Week 8 / Early Termination Visit no later than 5 days after the last dose of study drug.

At the start of the 6-Month Maintenance Period, subjects with healed EE will be randomized in a 1:1 ratio to one of the following 2 groups; the randomization will be stratified by baseline endoscopic findings (grades A/B or C/D).

- Group I: dexlansoprazole capsules (30 mg QD)
- Group II: placebo (QD)

During the 6-month Maintenance Period, study drug will be self-administered orally, QD in the morning before breakfast. Subjects will continue to document the presence and maximum severity of daytime and nighttime heartburn symptoms using a diary. Subjects will also record the use of rescue medication. Subject visits will be conducted at Months 1, 3 and 6, of the Maintenance Period to collect and/or dispense study drug, assess GERD symptoms, review concomitant medication use, and assess AEs. Endoscopies will be performed at Months 1 and 6/Final Visit to evaluate maintenance of healed EE. Subjects with endoscopic evidence of relapsed EE will be discontinued from the study.

At the Month 1 Visit, the subject will undergo a physical examination including vital signs, laboratory evaluations, endoscopy, and urine pregnancy test (all women of childbearing potential).

[figure not shown]

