10.2 Procedures

10.2.1 Collection and Reporting of AEs

10.2.1.1 PTE and AE Collection Period

Collection of PTEs will commence from the time the subject signs the informed consent to participate in the study and continue until the subject is first administered study medication or until screen failure. For subjects who discontinue prior to study medication administration, PTEs are collected until the subject discontinues study participation.

Collection of AEs will commence from the time that the subject is first administered study medication. Routine collection of AEs will continue until the Final Visit or Early Termination. A follow-up phone call will be made to each subject 5 to 10 days following the last dose of study drug to collect any AEs that may have occurred.

The stop date of the AEs/PTE is the date at which the subject recovered, the event resolved but with sequelae or the subject died.

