- (i) Study drug dispensed on Study Day -1 of the Screening Period Visit after the subject has completed all of the Screening Period procedures and subject has met all admission criteria for the study. Study drug will be self-administered on a daily basis for 8 weeks (Healing Period) and then 6 months (Maintenance Period).
- (j) Clinical laboratory tests include chemistry, hematology, and urinalysis. Hepatitis panel including HBsAg and HCV-antibody can be done either at the central laboratory or the local laboratory, depending on the site capability.
- (k) Women of childbearing potential only. Baseline serum pregnancy test will not be needed if the screening pregnancy test is within 14 days of baseline.
- (l) Healing therapy (blinded dexlansoprazole 60 mg capsules QD or lansoprazole 30 mg capsules QD).
- (m) Perform only if endoscopy confirms successful EE healing. Randomize to maintenance therapy, and dispense (blinded dexlansoprazole 30 mg capsules QD or matching placebo) accordingly. The first dose of maintenance therapy should be taken approximately 24 hours after last dose of healing therapy (ie, in the morning).
- (n) If subject has endoscopically-proven EE, they should be terminated from the study and undergo Final Visit (Month 6) Procedures.
- (o) Unscheduled Visit and Month 3 Visit endoscopies are optional, and may be warranted if subject presents with symptoms during EE Maintenance Period based on investigator's discretion. If subject has endoscopically-proven EE, the subject should be terminated from the study and undergo Final Visit (Month 6) /Early Termination Visit Procedures.
- (p) GERD symptoms should be assessed by an Investigator. If possible the same Investigator should perform these assessments for an individual subject throughout the study.
- (q) Dispense study drug if subject has not had endoscopically-proven relapse of EE.

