 - c) that personal information (including personal health information) may be added to Takeda's research databases for purposes of developing a better understanding of the safety and effectiveness of the study medication(s), studying other therapies for patients, developing a better understanding of disease, and improving the efficiency of future clinical studies;
 - d) that subjects agree not to restrict the use and disclosure of their personal information (including personal health information) upon withdrawal from the study to the extent that the restricted use or disclosure of such information may impact the scientific integrity of the research; and
 - e) that the subject's identity will remain confidential in the event that study results are published.

25. Women of childbearing potential (eg, nonsterilized, premenopausal women) who are sexually active must use adequate contraception (as defined in the informed consent) from Screening and throughout the duration of the study. Regular pregnancy tests will be performed throughout the study for all women of childbearing potential. If a subject is found to be pregnant during study, study medication will be discontinued and the investigator will offer the subject the choice to receive unblinded treatment information.
26. Men subjects must use adequate contraception (as defined in the informed consent) from Screening throughout the duration of the study. If the partner or wife of the subject is found to be pregnant during the study, the investigator will offer the subject the choice to receive unblinded treatment information.
27. A statement that clinical trial information from this trial will be publicly disclosed in a publicly accessible website, such as ClinicalTrials.gov.

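### The exemption of placebo subjects from pregnancy follow-up has no time limit, so it can release pregnancies that began on, or within 30 days of, active Healing drug

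*Protocol*

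**What the plan says.** Protocol Section 9.1.12 contains three rules that bear on the same subject.

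- **Reporting.** For a pregnancy that occurs while the subject is on active drug, or "within 30 days of the last dose of active study medication, the pregnancy should be reported immediately".
- **Follow-up.** "All reported pregnancies will be followed up to final outcome using the pregnancy form".
- **Exemption.** "Subjects randomized to placebo need not be followed". This comes directly after the instruction to break the individual blind if the subject wishes to know her treatment. It has no time limit and no condition on earlier active treatment.

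The design determines who the exemption covers. Both Healing arms are active (Section 6.1). Only subjects healed at Week 8 are randomized again, to dexlansoprazole 30 mg or placebo (Sections 6.1 and 8.3). There is no washout: "The first dose of maintenance therapy should be taken approximately 24 hours after last dose of healing therapy" (Appendix A, footnote m).

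Appendix C, item 25, provides that when a subject is found to be pregnant "the investigator will offer the subject the choice to receive unblinded treatment information". Item 26 makes the same offer when a male subject's partner becomes pregnant.

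**The concern.** The exemption is defined by randomized arm, whereas the reporting rule is defined by exposure. In this trial the two do not line up, because everyone randomized to placebo has just come off active drug. As written, the exemption reaches two kinds of pregnancy with active exposure:

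- one that begins in the first 30 days or so of placebo, within the section's own window after active drug;
- one conceived so late in Healing that the Week 8 tests could not yet detect it.

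At stake is the outcome of a pregnancy exposed to study drug. The adverse event system is only a partial substitute. A pregnant subject is withdrawn at once (Section 9.1.12). After that, "Routine collection of AEs will continue until the Final Visit or Early Termination" (Section 10.2.1.1), with one telephone call 5 to 10 days after the last dose. An SAE that comes to light later reaches the sponsor only if someone volunteers it and it is judged related to the study (Section 10.2.2). A birth would usually come months after that point, and a normal birth is not an SAE. The pregnancy form is therefore the only active route to a birth outcome, and it is the route the exemption allows a site to drop.

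**Working it through.** The plan gives no figure to reproduce here. The check is a comparison of the texts, some date arithmetic, and a rough count of events.

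**Dates.** Take the last Healing dose as day 0.

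- The first Maintenance dose is about 24 hours later (Appendix A, footnote m), so Maintenance Day 1 is day 1.
- The 30-day reporting window then runs over Maintenance Days 1 to 30.
- Month 6 is nominally Maintenance Day 180 (SAP Table 7.b), so the window is 30/180 = 17% of planned Maintenance time, for every placebo subject.

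**When a pregnancy would be found.**

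- The Week 8 visit includes "fasting serum gastrin, serum and urine pregnancy test (all women of childbearing potential), ECG and an endoscopy" (Section 6.1). A very recent conception would not show on those tests.
- The next scheduled test is the urine test at Month 1, plus or minus 7 days (Section 9.3.4.3). With Month 1 at Day 30 (SAP Table 7.b), that is Days 23 to 37.
- Subjects test negative before entering Healing. A pregnancy found at a Month 1 visit on or before Day 30 must therefore have begun during active Healing drug or within 30 days of it.

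**The rules applied to that pregnancy in a placebo subject.**

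| Rule in Section 9.1.12 | Result |
|---|---|
| Within 30 days of active drug | Report immediately |
| Reported pregnancies | Follow to final outcome |
| Randomized to placebo | Follow-up not required |

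The first two rules require follow-up and the third excuses it. The section does not say which prevails, and nothing elsewhere in the protocol limits the third.

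**Expected number of such pregnancies.**

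Expected count = placebo subjects × share who are women of childbearing potential × annual contraceptive failure rate × days/365.

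From the protocol:

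- 150 placebo subjects (Section 2.0);
- 30 days (Section 9.1.12);
- a 1% failure rate, from "An acceptable method of contraception is defined as one that has no higher than a 1% failure rate" (Section 9.1.11).

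Assumed, because the documents do not say:

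- a share of 10% to 50%;
- that the 1% is annual;
- 14 further days for late-Healing conceptions missed at Week 8;
- five times the 1% rate as a pessimistic case.

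| Days | Annual rate | Share 10% | Share 50% |
|---|---|---|---|
| 30 | 1% | 150 × 0.10 × 0.01 × 30/365 = 0.012 | 150 × 0.50 × 0.01 × 30/365 = 0.062 |
| 30 + 14 = 44 | 1% | 150 × 0.10 × 0.01 × 44/365 = 0.018 | 150 × 0.50 × 0.01 × 44/365 = 0.090 |
| 44 | 5% | 150 × 0.10 × 0.05 × 44/365 = 0.090 | 150 × 0.50 × 0.05 × 44/365 = 0.452 |

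Partner pregnancies are not counted. A loss of follow-up also requires that the site know the assignment and choose to use the exemption. The documents give no basis for putting numbers on those two steps.

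**The case against.** The strongest reply is that the section can be read as a coherent whole. The duty to report is triggered by exposure, applies at once and does not wait for unblinding. The final paragraph is mandatory and covers every reported pregnancy, whereas the placebo sentence only grants permission. On that reading, pregnancies in the active-drug window are reported and followed, and the exemption relieves sites only of later, placebo-only pregnancies. A site that follows everyone complies in any case.

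That is probably what was intended, but the text does not say it. The exemption follows directly on the unblinding instruction and reads naturally as an exception to the general duty. A site just told that its subject is on placebo has to infer the limit for itself.

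Two further objections have force.

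- **Chain of events.** The pregnancy must fall in a short window, the subject must accept unblinding, and the site must then rely on the exemption. Appendix C ensures that unblinding is offered, but nothing in the documents says how often it is accepted.
- **Upper figure.** The 0.45 rests on generous inputs. Section 4.1 says men develop erosive esophagitis more often than women, so a 50% share is high. The 14 days and the fivefold rate are not from the documents.

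Both reduce the expected consequence, and neither supplies the missing limit.

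The SAE definitions do cover congenital anomaly, spontaneous abortion, stillbirth and fetal death (Section 10.1.4). They do not create an active search for outcomes after a subject has left the study.

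**Conclusion.** The concern holds and is minor. Section 9.1.12 gives conflicting directions for a pregnancy in a placebo subject that began during active Healing drug or within 30 days of it, and the absence of a washout places every placebo subject in that window for about a month. The conflict rests on the protocol text and the dosing schedule alone and needs no assumption.

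The size does need assumptions: the share of women of childbearing potential, an annual reading of the 1% failure rate, and the 14 added days. On these, 0.01 to 0.09 pregnancies at risk are expected at the protocol's failure rate, and up to 0.45 in the pessimistic case. Expected losses of follow-up are smaller still. The effect is confined to safety follow-up and does not touch the efficacy analyses or the sample size.

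**What to change.** Limit the exemption by exposure as well as by arm, for example: *If the subject was randomized to placebo, a pregnancy that begins more than 30 days after the last active dose in either period need not be followed.* This keeps the relief for placebo-only pregnancies and agrees with the section's reporting window and its final paragraph. Deleting the sentence would also remove the conflict.

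The cost is one sentence in the protocol and at most a few additional pregnancy outcome forms.

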9.1.13 ECG Procedure

A standard 12-lead ECG will be recorded. The investigator (or a qualified observer at the investigational site) will interpret the ECG using 1 of the following categories: within normal limits, abnormal but not clinically significant, or abnormal and clinically significant.

The time that the ECG was performed will be recorded. The following parameters will be recorded on the eCRF from the subject's ECG tracing: heart rate, RR interval, PR interval, QT interval, and QRS interval.

As ECG tracings on thermal paper fade over time, any such tracings should be completely photocopied and both the original tracing and the counter-signed copy should be filed in the subject's medical record.

9.1.14 Documentation of Screen Failure

Investigators must account for all subjects who sign informed consent. If the subject is found to be not eligible at this visit, the investigator should complete the eCRF.

The IWRS should be contacted as a notification of screen failure.

The primary reason for screen failure is recorded in the eCRF using the following categories:

- Pretreatment event/AE.
- Did not meet inclusion criteria or did meet exclusion criteria.
- Significant protocol deviation.
- Lost to follow-up.
- Voluntary withdrawal.

- Study termination.
- Other.

Subject numbers assigned to subjects who fail screening should not be reused.

9.1.15 Documentation of Study Randomization

Only subjects who meet all of the inclusion criteria and none of the exclusion criteria are eligible for randomization into the Healing Period.

If the subject is found to be not eligible for randomization, the investigator should record the primary reason for failure on the applicable eCRF.

All screening procedures and test must be reviewed prior to randomization. Subjects who meet all the inclusion and none of the exclusion criteria will be randomized into the Healing Period via IWRS.

Subject with healed EE at the end of the Healing Period will be randomized again via the IWRS for the subsequent Maintenance Period.

Instructions on accessing and using the IWRS will be provided in a separate manual. Blinded details of subject treatment allocation (medication ID numbers) provided via the IWRS should be documented in the subject's medical record and/or eCRF.

9.1.16 Endoscopy

Endoscopy should be performed while subjects are fasted and according to the usual practice of the institution (ie, with regard to premedications or concomitant therapies, as long as they are not prohibited in Section 7.3 of this protocol).

The investigator (or designee) will record the results of endoscopy (including results of the LA classification and other gradings) performed promptly in the subject's medical record.

To ensure the accuracy of the EE evaluation according to LA grading, a 2nd review process of the endoscopic images will be established at each site. The 1st reviewer, ie, the endoscopist should take sufficient images or videotape the process at each endoscopic examination. The 2nd reviewer will evaluate the EE LA grading according to the endoscopic images.

- Preferably, the principal investigator performs as the 2nd reviewer and conducts the 2nd review in a timely manner after the endoscopy is performed by the 1st reviewer who is a subinvestigator in this study.
- In cases where the principal investigator is the 1st reviewer, a subinvestigator at the same site can be delegated as the 2nd reviewer and conducts the 2nd review in a timely manner.
- Only investigators (either principal investigators or subinvestigators) can be delegated as the 2nd reviewer.

If the LA grading by the 2 reviewers are consistent, this result becomes the final report. If not, the 2 reviewers will discuss their findings and reach a consensus which will then become the final report.

During Screening and at Week 8/Final Visit of the Healing Period, an endoscopy will be performed on all subjects to document the presence/absence of EE. Erosive esophagitis will be graded according to the LA Classification of Esophagitis Grading System ([Appendix E](#)).

The screening endoscopy must be performed within 14 days prior to randomization. Any reliable, documented results available from an endoscopy performed in a routine clinical setting (before signing of informed consent) within 14 days prior to randomization in the same institution will be accepted instead, given the invasive nature of the procedure.

Any Barrett's esophagus seen during screening endoscopy will exclude the subject from study. These endoscopic assessments will be recorded on the eCRF and a copy of the results should be kept with the subject's notes.

If a subject has endoscopically confirmed healing of EE at Week 8, they will be randomized into the Maintenance Period. During the Maintenance Period, endoscopies will be performed at Months 1 and 6/Final Visit to evaluate maintenance of healed EE. Subjects with endoscopic evidence of relapsed EE will be discontinued from the study.

Subjects who prematurely discontinue the study during the Maintenance Period should undergo Month 6 / Early Termination procedures no later than 5 days after the last dose of study drug, including the endoscopy.

Digital images of the current esophageal erosions should be captured and stored at the investigational site; images may be accessed by Takeda as necessary for quality assurance purpose.

